## Appendix 2. Clinical Laboratory Tests

### Hematology – local laboratory

- Leukocytes (WBC)
- Eosinophils
- Hematocrit (HCT)
- Neutrophilsa
- Basophils
- Platelets (PLT)
- Lymphocytes
- Erythrocytes (RBC)
- Monocytes
- Hemoglobin (HGB)

### Coagulation – local laboratory

Activated partial thromboplastin time (aPTT) or partial thromboplastin time (PTT)

International normalized ratio (INR) or prothrombin time (PT)

### Fibrinogen – local laboratory

### Clinical chemistry – local and central laboratoryb

#### *Serum concentrations of:*

- Alanine aminotransferase (ALT)
- Chloride
- Albumin
- Creatinine
- Alpha-fetoprotein (AFP; required only for patients with HCC)
- Creatine kinase (CK)
- Alkaline phosphatase
- Gamma glutamyl transferase (GGT)
- Aspartate aminotransferase (AST)
- Glucose, random
- Amylase
- Lipase
- Bicarbonate
- Potassium
- Bilirubin, direct
- Sodium
- Bilirubin, total
- Total protein
- Blood urea nitrogen (BUN) or blood urea
- C-reactive protein
- Calcium

### TSH and free T4 – central laboratory

### Erythrocyte sedimentation rate (ESR) – local laboratory

### C3a complement – central laboratory

### C-ANCA/P-ANCA/Troponin-I – central laboratory

### Tumor markers – local laboratory

### Urinalysis – local laboratory

A microscopic examination is required for abnormal results. Microscopy should be used as appropriate to investigate white blood cells and use the high-power field for red blood cells. Perform the 24-hour urine protein analysis if urine protein is  $\geq 2+$  at baseline or during study treatment

- Bilirubin
- Glucose
- Protein
- Blood
- Ketones
- Specific gravity
- Color and appearance
- pH
- Urine leukocyte esterase

### Pregnancy test (for female patients of childbearing potential) – local laboratory

- Urine pregnancy test at a minimum sensitivity of 25 IU/L or equivalent units of  $\beta$ -hCG. If urine pregnancy results cannot be confirmed as negative, a serum pregnancy test will be required

CCI

CCI

Abbreviations: DNA = deoxyribonucleic acid; Ig = immunoglobulin; LY = LY3434172; PK = pharmacokinetic; RBC = red blood cells; RNA = ribonucleic acid; T4 = thyroxine; TSH = thyroid-stimulating hormone; WBC = white blood cells.

**Note:** Study eligibility and decisions about treatment will be based on local laboratory results.

- a Neutrophils reported by automated differential hematology instruments include both segmented and band forms. When a manual differential is needed to report the neutrophils, the segmented and band forms should be added together and recorded on the CRF, unless the CRF specifically provides an entry field for bands.
- b Performed centrally (required) and locally if clinically indicated.
- c CCI

---

## Appendix 3. Study Governance, Regulatory and Ethical Considerations

---

### **Informed Consent**

The investigator is responsible for:

- ensuring that the patient understands the nature of the study, the potential risks and benefits of participating in the study, and that their participation is voluntary
- ensuring that informed consent is given by each patient. This includes obtaining the appropriate signatures and dates on the ICF prior to the performance of any study protocol procedures and prior to the administration of study treatment.
- answering any questions the patient may have throughout the study and sharing in a timely manner any new information that may be relevant to the patient's willingness to continue the patient's participation in the study.
- providing a copy of the ICF to the patient and retaining a copy of the signed ICF in the site file

### **Ethical Review**

Documentation of ERB/IRB approval of the protocol and the ICF must be provided to Lilly before the study may begin at the investigative site(s). Lilly or its representatives must approve all ICFs, including any changes made by the ERBs/IRBs, before it is used at the investigative site(s). All ICFs must be compliant with the ICH guideline on GCP.

The study site's ERB/IRB should be provided with the following:

- the protocol, protocol amendments, and relevant protocol addenda, and the current IB and updates during the course of the study
- ICF
- other relevant documents (for example, curricula vitae, advertisements)

### **Regulatory Considerations**

This study will be conducted in accordance with:

- consensus ethics principles derived from international ethics guidelines, including the Declaration of Helsinki and Council for International Organizations of Medical Sciences International Ethical Guidelines
- the ICH GCP guidelines
- applicable laws and regulations

The investigator or designee will promptly submit the protocol to applicable ERB(s).

Some of the obligations of Lilly will be assigned to a third party organization.

### **Investigator Information**

Licensed physicians with a specialty in oncology will participate as investigators in this clinical study

### **Protocol Signatures**

Lilly's responsible medical officer will approve the protocol, confirming that, to the best of his or her knowledge, the protocol accurately describes the planned design and conduct of the study.

After reading the protocol, each principal investigator will sign the protocol signature page and send a copy of the signed page to a Lilly representative.

### **Final Report Signature**

The CSR coordinating investigator will sign the final CSR for this study, indicating agreement that, to the best of his or her knowledge, the report accurately describes the conduct and results of the study. If this investigator is unable to fulfill this function, another investigator will be chosen by Lilly to serve as the CSR coordinating investigator.

Lilly's responsible medical officer and statistician will approve the final CSR for this study, confirming that, to the best of his or her knowledge, the report accurately describes the conduct and results of the study.

### **Data Quality Assurance**

To ensure accurate, complete, and reliable data, Lilly or its representatives will do the following:

- provide instructional material to the study sites, as appropriate
- provide sponsor start-up training to instruct the investigators and study coordinators. This training will give instruction on the protocol, the completion of the CRFs, and study procedures.
- make periodic visits to the study site
- be available for consultation and stay in contact with the study site personnel by mail, telephone, and/or fax
- review and verify data reported to detect potential errors

In addition, Lilly or its representatives will periodically check a sample of the patient data recorded against source documents at the study site. The study may be audited by Lilly or its representatives and/or regulatory agencies at any time. Investigators will be given notice before an audit occurs.

The investigator will keep records of all original source data. This might include laboratory tests, medical records, and clinical notes. If requested, the investigator will provide the sponsor, applicable regulatory agencies, and applicable ERBs with direct access to original source documents.

**Data Capture Systems**

The investigator is responsible for ensuring the accuracy, completeness, legibility, and timeliness of the data reported to the sponsor.

An electronic data capture system (EDC) will be used in this study for the collection of CRF data. The investigator maintains a separate source for the data entered by the investigator or designee into the sponsor-provided EDC system. The investigator is responsible for the identification of any data to be considered source and for the confirmation that data reported are accurate and complete by signing the CRF.

Additionally, clinical outcome assessment (COA) data (questionnaires, scales, self-reported diary data, rating scales etc.) will be collected by the subject/investigator site personnel, via a paper source document and will be transcribed by the investigator site personnel into the EDC system.

Data collected via the sponsor-provided data capture system(s) will be stored at third parties. The investigator will have continuous access to the data during the study and until decommissioning of the data capture system(s). Prior to decommissioning, the investigator will receive an archival copy of pertinent data for retention.

Data managed by a central vendor, such as laboratory test data, will be stored electronically in the central vendor's database system and reports/electronic transfers will be provided to the investigator for review and retention. Data will subsequently be transferred from the central vendor to the Lilly data warehouse.

Data from complaint forms submitted to Lilly will be encoded and stored in the global product complaint management system.

**Study and Site Closures****Discontinuation of Study Sites**

Study site participation may be discontinued if Lilly or its designee, the investigator, or the ERB/IRB of the study site judges it necessary for medical, safety, regulatory, ethical, or other reasons consistent with applicable laws, regulations, and GCP.

**Discontinuation of the Study**

The study will be discontinued if Lilly or its designee judges it necessary for medical, safety, regulatory, or other reasons consistent with applicable laws, regulations, and GCP.

---

## Appendix 4. Sampling Schedule

---

Pharmacokinetic, Immunogenicity and Biomarker samples will be collected for all patients receiving LY3434172.

Preferred time windows for each PK/IG sample collection are provided in the tables in this section. While best effort should be done to draw the blood samples within the time windows provided, it is more important to ensure predose sample is actually collected before the start of first infusion of the day and postdose samples are collected after the respective infusion has completed. It is also equally important to record ACTUAL date and time of blood sample collection on the Requisition Form AFTER drawing the sample (that is, do not record planned time of collection) and to record the ACTUAL infusions start and end dates and times on the eCRF in order to facilitate the data analyses.

Blood sample collection must be from the opposite arm to that used for study drug infusion. If drug was administered via a central venous catheter, the sample collection should be from a different site.

In the event of an infusion-related reaction (IRR), blood samples will be collected for PK, IG and exploratory immune safety analyses at the following time points, as close as possible to: (i) the onset of the IRR, (ii) the resolution of the IRR, and (iii) 30 [ $\pm 3$ ] days following the IRR.

CCI

**Pharmacokinetic, Immunogenicity, Biomarker, and ECG Collection Time Points**  
**Cohorts with Q2W Dosing (Cohort A1, A2, A3, A4, A5, and A6)**

Pharmacokinetic, Immunogenicity, Biomarker, and ECG Collection Time Points Cohorts with Q2W Dosing (Cohort A1, A2, A3, A4, A5, and A6)													
Cycle/Day	Study Day	Sample Time (Relative to the END of LY3434172 Infusion)	PK a	IG a	Whole Blood (PGx)	Biomarker Collection						ECG	
						Plasma	Ex vivo	Whole Blood & PBMC b	Serum	Tissue	sPD-1 and sPD-L1		
Baseline		≤28 days prior to C1D1  • ECG: 2-3 sets of ECGs (each set is a triplicate), with approximately 15 minutes between each set. d Tumor tissue: required see Section 9.8.1.								X		X	X
Baseline		≤7 days prior to C1D1					X	X					
C1D1	1	• 0 hour predosee • PK, IG, and biomarkers • ECG: 2-3 sets of ECGs (each set is a triplicate), with approximately 15 minutes between each set. d Before blood draw.	X	X	X	X	X	X	X		X	X	
C1D1		• 1 hour post LY3434172 infusionf • ECG (triplicate) Before blood draw. d	X				X	X	X		X	X	

Pharmacokinetic, Immunogenicity, Biomarker, and ECG Collection Time Points Cohorts with Q2W Dosing (Cohort A1, A2, A3, A4, A5, and A6)												
Cycle/Day	Study Day	Sample Time (Relative to the END of LY3434172 Infusion)	PK a	IG a	Whole Blood (PGx)	Biomarker Collection						
						Plasma	Ex vivo	Whole Blood & PBMC b	Serum	Tissue	sPD-1 and sPD-L1	Stool c
C1D1	1	
 
• 3 hours post LY3434172 infusionf
 
• ECG (triplicate) Before blood drawd
 
	X					X	X		X	
C1D2	2	
 
• 24 hours post LY3434172 infusionf
 
• ECG (triplicate) Before blood draw.d
 
	X				X	X	X		X	X
C1D4	4	72 hours post LY3434172 infusion f	X								X	
C1D8	8	168 hours post LY3434172 infusion f	X	X		X	X	X	X		X	
C1D15	15	
 
• 0 hour predosee
 
• PK, IG, and biomarkers
 
	X	X			X	X	X		X	
C1D15	15	
 
• 1 hour post LY3434172 infusionf
 
• ECG (triplicate) Before blood draw.d
 
	X				X (only cohort A1)		X (only A1)		X	X
C1D15	15	
 
• 3 hours post LY3434172 infusionf
 
	X								X	
C1D16	16	
 
• 24 hours post LY3434172 infusionf
 
	X				X (only cohort A1)		X (only A1)		X	

Pharmacokinetic, Immunogenicity, Biomarker, and ECG Collection Time Points Cohorts with Q2W Dosing (Cohort A1, A2, A3, A4, A5, and A6)												
Cycle/Day	Study Day	Sample Time (Relative to the END of LY3434172 Infusion)	PK a	IG a	Whole Blood (PGx)	Biomarker Collection						
						Plasma	Ex vivo	Whole Blood & PBMC b	Serum	Tissue	sPD-1 and sPD-L1	Stool c
C1D22	22	168 hours post LY3434172 infusion f	X			X (only cohort A1)	X	X (only A1)		X		
C2D1	29	• 0 hour predosee • PK, IG, and biomarkers	X	X		X	X	X	X	X g	X	X
C2D1	29	• 1 hour post LY3434172 infusionf • ECG (triplicate) Before blood draw. d	X								X	X
C2D2	30	• 24 hours post LY3434172 infusionf	X								X	
C2D15	43	• 0 hour predosee	X			X (only cohort A1)	X	X (only A1)		X		
C2D15	43	• 1 hour post LY3434172 infusionf • ECG (triplicate) Before blood draw. d	X							X		X
C2D16	44	• 24 hours post LY3434172 infusionf	X							X		
C3D1	57	• 0 hour predosee • PK, IG, and biomarkers	X	X		X		X	X	X		

Pharmacokinetic, Immunogenicity, Biomarker, and ECG Collection Time Points Cohorts with Q2W Dosing (Cohort A1, A2, A3, A4, A5, and A6)												
Cycle/Day	Study Day	Sample Time (Relative to the END of LY3434172 Infusion)	PK a	IG a	Whole Blood (PGx)	Biomarker Collection						ECG
						Plasma	Ex vivo	Whole Blood & PBMC b	Serum	Tissue	sPD-1 and sPD-L1	
C3D1	57	
 
• 1 hour post LY3434172 infusionf
 
• ECG (triplicate) Before blood draw.d
 
	X								X	X
C4D1	85	
 
• 0 hour predosee
 
• PK and biomarkers
 
	X	X							X	
C4D1	85	
 
• 1 hour post LY3434172 infusion
 
• ECG (single)
 
										X
C5D1	113	
 
• 0 hour predosee
 
• PK and biomarkers
 
	X	X							X	
C5D1	113	
 
• 1 hour post LY3434172 infusion
 
• ECG (single)
 
										X
C6D1	141	
 
• 0 hour predosee
 
• PK and biomarkers
 
	X	X							X	
C6D1	141	
 
• 1 hour post LY3434172 infusion
 
• ECG (single)
 
										X
C7D1; then, Q3 (C10D1...)	169, 197...	
 
• 0 hour predosee
 
• PK and biomarkers
 
	X	X							X	

Pharmacokinetic, Immunogenicity, Biomarker, and ECG Collection Time Points Cohorts with Q2W Dosing (Cohort A1, A2, A3, A4, A5, and A6)												
Cycle/Day	Study Day	Sample Time (Relative to the END of LY3434172 Infusion)	PK a	IG a	Whole Blood (PGx)	Biomarker Collection						
						Plasma	Ex vivo	Whole Blood & PBMC b	Serum	Tissue	sPD-1 and sPD-L1	Stool c
When/if any DLT or DLT equivalent occurs		Anytime	X	X							X	
Last LY3434172 dose (if known)		
 
0 hour predosee
 
PK, IG, and biomarkers
 
	X	X							X	
30 days post last LY3434172 dose		Anytime f 
 
ECG (single). Before blood draw.
 
	X			X					X	X
60 days post last LY3434172 dose		Anytime f 
 
ECG (single). Before blood draw.
 
	X	X							X	X
90 days post last LY3434172 dose		Anytime f 
 
ECG (single). Before blood draw.
 
	X								X	X
Disease Progression		Anytime before start of next anticancer treatment. 
 
Highly recommended
 
				X				X (optional)	X	

Abbreviations: ADA = antidrug antibody; C = Cycle; D = Day; DLT = dose-limiting toxicity; ECG = electrocardiogram; IG = immunogenicity;

IRR = infusion-related reaction; PGx = pharmacogenomics; PK = pharmacokinetics; Q = every; W = week.

a In the event of an infusion-related reaction (IRR), blood samples will be collected for PK, IG and exploratory immune safety analyses at the following time points, as close as possible to: (i) the onset of the IRR, (ii) the resolution of the IRR, and (iii) 30 [ $\pm$ 3] days following the IRR. [REDACTED]

- b For exploratory research, including but not limited to immunophenotyping.
- c Fecal collections will begin at baseline with any new patients starting the trial at that time, and as the collection materials become available.
- d Triplicate ECGs: the 3 replicates should be approximately 1 minute apart, with all 3 replicates within a set conducted within a 5-minute timeframe.
- e Collect samples in the morning of infusion day prior to the start of first infusion of the day.
- f The 1-, 3-, 24-, 72-, and 168-hour samples are relative to the END of the corresponding dosing event. These samples must be collected after completion of the infusion. Their sampling windows are  $\pm$ 15 minutes (1- and 3-hour),  $\pm$  4 hours (24-hour),  $\pm$  24 hours (72- and 168-hour), respectively. The samples at 30, 60, and 90 days post last LY3434172 dose have sampling windows of  $\pm$ 7 days.
- g Tissue biopsy sample within 3 days prior to C2D1.

**Pharmacokinetic, Immunogenicity, Biomarker, and ECG Collection Time Points**  
**Cohorts with Q3W Dosing (Cohort A7 and A8)**

Pharmacokinetic, Immunogenicity, Biomarker, and ECG Collection Time Points Cohorts with Q3W Dosing (Cohort A7 and A8)													
Cycle/Day	Study Day	Sample Time (Relative to the END of LY3434172 Infusion)	PK a	IG a	Whole Blood (PGx)	Biomarker Collection						Stool c	ECG
						Plasma	Ex vivo	Whole Blood & PBMC b	Serum	Tissue	sPD-1 and SPD-L1		
Baseline		
≤28 days prior to C1D1
 
 
ECG: 2-3 sets of ECGs (each set is a triplicate), with approximately 15 minutes between each set.d
 
 
Tumor tissue: required see Section 9.8.1
								X		X	-X
Baseline		≤7 days prior to C1D1					X	X					
C1D1	1	
 
0 hour predosee
 
PK, IG, and biomarkers
 
ECG: 2-3 sets of ECGs (each set is a triplicate), with approximately 15 minutes between each set. Before blood draw.d
 
	X	X	X	X	X	X	X		X		X

Pharmacokinetic, Immunogenicity, Biomarker, and ECG Collection Time Points Cohorts with Q3W Dosing (Cohort A7 and A8)													
Cycle/Day	Study Day	Sample Time (Relative to the END of LY3434172 Infusion)	PK a	IG a	Whole Blood (PGx)	Biomarker Collection						Stool c	ECG
						Plasma	Ex vivo	Whole Blood & PBMC b	Serum	Tissue	sPD-1 and SPD-L1		
C1D1	1	
 
• 1 hour post LY3434172 infusionf
 
• ECG (triplicate). Before blood draw.d
 
	X				X	X	X		X		X
C1D1	1	
 
• 3 hours post LY3434172 infusionf
 
• ECG (triplicate). Before blood draw.d
 
	X					X	X		X		X
C1D2	2	
 
• 24 hours post LY3434172 infusionf
 
• ECG (triplicate). Before blood draw.d
 
	X				X	X	X		X		X
C1D4	4	72 hours post LY3434172 infusion f	X								X		
C1D8	8	168 hours post LY3434172 infusion f	X	X		X	X	X	X		X		
C1D15	15	336 hours post LY3434172 infusion f	X					X			X		

Pharmacokinetic, Immunogenicity, Biomarker, and ECG Collection Time Points Cohorts with Q3W Dosing (Cohort A7 and A8)														
Cycle/Day	Study Day	Sample Time (Relative to the END of LY3434172 Infusion)	PK a	IG a	Whole Blood (PGx)	Biomarker Collection							Stool c	ECG
						Plasma	Ex vivo	Whole Blood & PBMC b	Serum	Tissue	sPD-1 and SPD-L1			
C2D1	22	
 
• 0 hour predosee
 
• PK, IG, and biomarkers
 
	X	X		X	X	X	X		X			
C2D1	22	
 
• 1 hour post LY3434172 infusionf
 
• ECG (triplicate). Before blood draw.d
 
	X								X		X	
C2D1	22	
 
• 3 hours post LY3434172 infusionf
 
	X								X			
C2D2	24	24 hours post LY3434172 infusion f	X								X			
C2D8	30	168 hours post LY3434172 infusion f	X	X				X			X			
C3D1	43	
 
• 0 hour predosee
 
• PK, IG, and biomarkers
 
	X	X		X	X	X	X	X g	X	X		

Pharmacokinetic, Immunogenicity, Biomarker, and ECG Collection Time Points Cohorts with Q3W Dosing (Cohort A7 and A8)													
Cycle/Day	Study Day	Sample Time (Relative to the END of LY3434172 Infusion)	PK a	IG a	Whole Blood (PGx)	Biomarker Collection						Stool c	ECG
						Plasma	Ex vivo	Whole Blood & PBMC b	Serum	Tissue	sPD-1 and SPD-L1		
C3D1	43	
 
• 1 hour postdose infusionf
 
• ECG (triplicate). Before blood draw.d
 
	X								X		X
C4D1	64	
 
• 0 hour predosee
 
• PK, and IG
 
	X	X							X		
C6D1		
 
• 0 hour predosee
 
• PK: collect sample for all patients
 
	X	X							X		
C8D1; then, Q4C (Cycle 12...)	148, 232...	
 
• 0 hour predosee
 
• PK: collect PK sample for all patients
 
	X	X							X		
When/if any DLT or DLT equivalent occurs		Anytime	X	X							X		
Last LY3434172 dose (if known)		
 
• 0 hour predosee sample
 
• PK, IG, and biomarkers
 
	X	X							X		
30 days post last LY3434172 dose		Anytime f 
 
• ECG (single). Before blood draw.
 
	X			X					X		X

Pharmacokinetic, Immunogenicity, Biomarker, and ECG Collection Time Points Cohorts with Q3W Dosing (Cohort A7 and A8)														
Cycle/Day	Study Day	Sample Time (Relative to the END of LY3434172 Infusion)	PK a	IG a	Whole Blood (PGx)	Biomarker Collection							Stool c	ECG
						Plasma	Ex vivo	Whole Blood & PBMC b	Serum	Tissue	sPD-1 and SPD-L1			
60 days post last LY3434172 dose		Anytime f • ECG (single). Before blood draw.	X	X							X		X	
90 days post last LY3434172 dose		Anytime f • ECG (single). Before blood draw.	X								X		X	
Disease progression		Anytime before next anticancer treatment. • Highly recommended				X				X (optional )		X		

Abbreviations: ADA = antidrug antibody; C = Cycle; D = Day; DLT = dose-limiting toxicity; ECG = electrocardiogram; IG = immunogenicity;

IRR = infusion-related reaction; PGx = pharmacogenomics; PK = pharmacokinetics; Q = every; W = week.

a In the event of an infusion-related reaction (IRR), blood samples will be collected for PK, IG and exploratory immune safety analyses at the following time points, as close as possible to: (i) the onset of the IRR, (ii) the resolution of the IRR, and (iii) 30 [ $\pm$ 3] days following the IRR. CCI

b For exploratory research, including but not limited to immunophenotyping.

c Fecal collections will begin at baseline with any new patients starting the trial at that time, and as the collection materials become available.

d Triplicate ECGs: the 3 replicates should be approximately 1 minute apart, with all 3 replicates within a set conducted within a 5-minute timeframe.

e Collect samples in the morning of infusion day prior to the start of first infusion of the day.

f The 1-, 36-, 24-, 72-, 168- and 336-hour samples are relative to the END of the corresponding dosing event. They must be collected after the completion of the infusion. Their sampling windows are  $\pm$ 15 minutes (1- and 3-hour),  $\pm$  4 hours (24-hour),  $\pm$  24 hours (72-, 168- and 336-hour), respectively. The samples at 30, 60, and 90 days post last LY3434172 dose have sampling windows of  $\pm$  7 days.

g Tissue biopsy sample within 3 days prior to C3D1.

## Appendix 5.      **Restricted and Prohibited Concomitant Medications**

The table below describes the drug class and associated medications that will be restricted during the study treatment period. Patients who, in the opinion of the investigator, require the use of any of the prohibited treatments for clinical management should be discontinued from the trial. Patients may receive other supportive therapy that the investigator deems to be medically necessary.

Therapy	As Needed	Chronic Use	Exceptions or Conditions for Use
Antiplatelet therapy	Yes	Yes, with restrictions	Chronic use of aspirin up to 325 mg/day is permitted
Anticoagulation therapy	No	Yes, with restrictions	Patients who are on full-dose anticoagulation must be on a stable dose (minimum duration 14 days) of oral anticoagulant or low-molecular-weight heparin or similar agent. If on warfarin, the patient must have an INR of $\leq 3$ and no active bleeding or pathological condition present that carries a high risk of bleeding (for example, tumor involving major vessels or known varices).
Colony-stimulating factors	Yes	No	Follow local guidelines. No prophylactic use
Erythroid growth factors	Yes	No	Follow local guidelines
Experimental medicines or investigational agents	No	No	
Glucocorticoids	Yes, with restrictions	Yes, with restrictions	Use of corticosteroids for the management of investigational product-related AEs or in patients with contrast allergies is acceptable. A temporary course of corticosteroids will be allowed for other indications, at the discretion of the principal investigator (for example, chronic obstructive pulmonary disease, radiation, nausea). Systemic corticosteroids doses should not exceed 10 mg/day of prednisone or equivalent (except as stated otherwise in this protocol). The use of physiologic doses of corticosteroids may be approved after consultation with Lilly. The use of topical, ophthalmic, inhaled, and intranasal corticosteroids is permitted.

Therapy	As Needed	Chronic Use	Exceptions or Conditions for Use
Immunosuppressive medications other than glucocorticoids (including, but not limited to methotrexate, azathioprine, and TNF- $\alpha$ blockers)	No	No	Use of immunosuppressive medications for the management of AEs related to LY3434172 or in patients with contrast allergies is acceptable
NSAIDs	Yes	No	See guidance for aspirin on the “antiplatelet therapy” line above. Chronic use of other NSAIDs is not permitted. However, in certain medical situations, NSAIDs may be the best treatment option (for example, for pain management) and are therefore permissible as needed.

Abbreviations: AE = adverse event; INR = international normalized ratio; NSAIDs = nonsteroidal anti-inflammatory drugs; TNF = tumor necrosis factor.

---

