## 7.7. Concomitant Therapy

[Appendix 5](#) describes medications, treatments, and drug classes that are restricted or prohibited for use during the study treatment period, including exceptions and conditions. There are no prohibited therapies during the post discontinuation follow-up period. Patients who, in the opinion of the investigator, require the use of any of the prohibited treatments for clinical

management should be discontinued from the trial. Patients may receive other supportive therapy that the investigator deems to be medically necessary.

In general, medications or live vaccinations specifically prohibited in the exclusion criteria are not allowed during the ongoing trial except with approval from Lilly CRP/CRS.

No other chemotherapy, systemic radiotherapy, immunotherapy, cancer-related hormone therapy, experimental drugs, herbal supplements intended to treat cancer will be permitted while the patients are on this study.

Palliative radiation therapy to small areas of painful metastases that cannot be adequately managed with systemic or local analgesics is permitted after discussion with and agreement of the Lilly CRP/CRS.

In addition, any disease progression requiring other forms of specific antitumor therapy will also necessitate early discontinuation from study treatment. Appropriate documentation for all forms of premedication, supportive care, and concomitant medications must be captured on the eCRF. Replacement hormonal therapy initiated before study entry will be allowed.

Patients should receive full supportive care. The use of granulocyte-colony stimulating factor (G-CSF) is permitted at the discretion of the investigator based on ASCO (Smith et al. 2015) and European Society for Medical Oncology (Crawford et al. 2010) guidelines.

If clinically indicated at any time during the study, erythropoietin and packed red blood cell transfusions may be used according to ASCO guidelines (Rizzo et al. 2008). Prophylactic antibiotic treatment should be consistent with ASCO guidelines (Flowers et al. 2013).

All concomitant medications should be recorded throughout the patient's participation in the study.

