**Figure JZEA.2. Continued access diagram.**

## 8. Discontinuation Criteria

The reasons for treatment and study discontinuation and the dates of discontinuation will be collected for all patients.

Patients who discontinue during the study treatment period, whether or not they received study treatment, will have follow-up procedures performed as shown in the Schedule of Activities (Section 2).

If a patient withdraws informed consent, he or she must not be contacted unless he or she has explicitly provided permission and consent. Lilly may continue to use previously collected medical research data prior to the withdrawal consistent with the original authorization.

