### 8.1. Discontinuation from Study Treatment

Patients will be discontinued from study treatment in the following circumstances:

- the patient is enrolled in any other clinical study involving an investigational product or any other type of medical research judged not to be scientifically or medically compatible with this study.
- the patient becomes pregnant during the study
- the patient is significantly non-compliant with study procedures and/or treatment as described in Section 7.6
- The patient experiences a DLT (see Section 7.2.2.2) during Cycle 1, a DLT-ET (see Section 7.2.2.2.2), or other unacceptable toxicity
- the patient requires a dose delay of >28 days for Q2W schedule and >21 days for Q3W schedule, except as described in Section 7.4
- the patient, for any reason, requires treatment with another therapeutic agent that has been demonstrated to be effective for treatment of the study indication. Discontinuation from study treatment will occur prior to introduction of the new agent
- the investigator decides that the patient should be discontinued from study treatment, for reasons such as but not limited to confirmed disease progression (see Section 9.1.1).
- the patient requests to be discontinued from study treatment

Patients who are discontinued from study treatment will have follow-up procedures performed as shown in the Schedule of Activities (Section 2).

Discontinuation of study treatment may be considered for patients who meet all of the following criteria:

- have a confirmed complete response (CR), **and**
- have received study treatment for at least 24 weeks, **and**
- have received at least 2 cycles of study treatment beyond the date when the initial CR was declared.

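### Section 7.7 and Appendix 5 take a patient who needs a prohibited treatment off the trial, whereas Section 8.1 stops only study treatment in overlapping cases; a site could end survival follow-up early

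*Protocol*

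**What the plan says.** Appendix 5 of the protocol states that patients who, in the investigator's opinion, "require the use of any of the prohibited treatments for clinical management should be discontinued from the trial". Section 7.7 carries the same sentence, ending "management should be discontinued from the trial".

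Other current text uses a different term or assumes a different outcome:

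- Section 7.7, immediately before that sentence: "There are no prohibited therapies during the post discontinuation follow-up period".
- Section 7.7, later: "any disease progression requiring other forms of specific antitumor therapy will also necessitate early discontinuation from study treatment".
- Section 8, as a general rule: "Patients who discontinue during the study treatment period, whether or not they received study treatment, will have follow-up procedures performed" according to the Schedule of Activities.
- Section 8.1 lists, among reasons to stop study treatment, that "the patient, for any reason, requires treatment with another therapeutic agent that has been demonstrated to be effective for treatment of the study indication". Its first item covers enrolment in another investigational-product study. Follow-up per Section 2 applies to everyone taken off study treatment.
- Section 8.2 lists reasons for leaving the study. Need for a prohibited treatment is not among them, although an investigator's decision is. It assigns end-of-study procedures from Section 2, which has no visit of that name.
- Table JZEA.3 collects survival and subsequent anticancer therapy at every follow-up visit. Note b ends long-term follow-up at death, study withdrawal or loss to follow-up.

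**The concern.** The protocol treats stopping study treatment and leaving the study as two events. Section 8 collects reasons and dates for both, and Sections 8.1 and 8.2 give separate lists. A reason meant to trigger both, such as pregnancy, appears in both lists. Need for a prohibited treatment is named in neither, so a site cannot settle what leaving the trial means by looking it up.

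The choice matters downstream. If the site records study discontinuation:

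- Long-term survival contacts could stop (Table JZEA.3, note b), and OS would then be censored at the last date known alive (SAP 6.13.7).
- Once the disposition eCRF is complete, the site is no longer obliged to look actively for adverse events (Section 9.2.1). Section 7.4 warns that immune-related events can appear months after the last dose, and safety is the primary objective.
- The registry participant flow, which SAP 6.19 bases on leaving the study rather than stopping treatment, could change.

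**Working it through.** The plan gives no figure on this point. The check is a comparison of texts, followed by a count of the contacts at risk.

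**Comparison by type of treatment**

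| Need | Under the Section 7.7 and Appendix 5 sentence | Under other text | Result |
|---|---|---|---|
| Experimental agent (Appendix 5 allows neither as-needed nor chronic use) | Off the trial | Section 8.1, first item: a patient enrolled in another investigational-product study stops study treatment, with follow-up | Conflict |
| Other anticancer therapy (barred by Section 7.7) | Off the trial | Section 8.1 effective-agent item and Section 7.7 progression sentence: study treatment stops. Table JZEA.3 records the new therapy during follow-up | Conflict |
| Other classes, such as chronic NSAIDs or immunosuppressants outside the stated exceptions | Off the trial | No named item in 8.1 or 8.2; the investigator-decision item in either list could be used | Ambiguity |

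**Long-term contacts at risk, per patient**

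Inputs:

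- d = days from first dose to the decision to stop treatment.
- Short-term follow-up ends at the 90-day visit (Table JZEA.3, note a).
- Long-term contacts follow every 90 days (Table JZEA.3).
- OS is followed for 12 months after the last patient enters treatment (Section 10.3.2), taken as day 365 for that patient.
- Visit windows are ignored.

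The k-th long-term contact falls on day d + 90 + 90k. It counts if d + 90 + 90k ≤ 365, that is, if d ≤ 275 − 90k.

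- k = 3: d ≤ 275 − 270 = 5
- k = 2: d ≤ 275 − 180 = 95
- k = 1: d ≤ 275 − 90 = 185

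| Treatment stops on day | Long-term contacts at risk |
|---|---|
| 0 to 5 | 3 |
| 6 to 95 | 2 |
| 96 to 185 | 1 |
| after 185 | 0 |

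Example: d = 28 puts contacts on days 208, 298 and 388. The third is past day 365, so 2 are at risk.

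A patient who entered e days before the last one has a limit of 365 + e, so each 90 days of earlier entry adds one contact. These are maxima, because Section 7.8.1.1 ends long-term follow-up for everyone still in it when the continued access period begins.

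**The case against.** The strongest reply is that context already settles the wording. Appendix 5 limits its restrictions to the study treatment period. The sentence before the disputed one in Section 7.7 assumes a patient who has stopped and is still being followed. Section 8 orders follow-up for anyone who discontinues during treatment. Section 8.1 also lets the investigator stop study treatment "for reasons such as but not limited to confirmed disease progression". A careful site could reach the right result.

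This reply limits the harm but does not remove the conflict: the literal instruction still differs from Section 8.1, and the investigator-decision item in Section 8.2 is equally available to a site that takes it literally.

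A reader might go further and infer that survival follow-up would necessarily end. The documents do not support that:

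- Study withdrawal in note b may mean the patient's own withdrawal. The next sentence of the note bars follow-up only after withdrawal of consent, and so does Section 8.
- Apart from the continued-access visits, the only post-treatment schedule in Section 2 is Table JZEA.3, so the end-of-study procedures of Section 8.2 may lead back to it.

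Nor is a change in the registry count certain. SAP 6.19 also treats a patient as a completer if information for the primary and secondary endpoints has been observed, and OS is neither.

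**Conclusion.** The concern holds as a minor one. The sentence in Section 7.7 and Appendix 5 conflicts with Section 8.1, and with Section 7.7 itself, for investigational and other anticancer agents, and is ambiguous for other classes. Read as study discontinuation, it could cost up to 3 long-term survival contacts for a last-entered patient, and 2 for most stops in the first three months, under the assumptions above. The documents give no rate of prohibited-treatment use, so neither the number of patients affected nor any bias in OS can be estimated.

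Three further inferences are not supported:

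- Loss of the 30-, 60- and 90-day adverse-event visits is not ordered. Section 8 and note a of Table JZEA.3 still provide them, and Section 9.2 keeps serious or related events under follow-up. They are at risk only if the disposition eCRF is completed early.
- The sentence is not the only rule for any drug class. Appendix 5 permits immunosuppressants for drug-related adverse events, and Section 7.7 allows G-CSF, erythropoietin and some exceptions approved by the sponsor.
- No effect on PFS or duration of response is shown. OS is exploratory, and SAP 6.6 plans no hypothesis testing.

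**What to change.** In Section 7.7 and Appendix 5, replace the instruction to discontinue the patient from the trial with an instruction to discontinue study treatment (Section 8.1) and follow the patient per Table JZEA.3. Add need for a prohibited treatment to the Section 8.1 list.

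The cost is two reworded sentences and one added item. The follow-up visits are already scheduled, so no new visit or data collection is needed.
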